Individuals with single large-scale mitochondrial DNA deletions	30	33 (accounting for 10% attrition or unusable data)	18 to 60

Description of subject population:

We will investigate individuals carrying a single large-scale mtDNA deletions that causes CPEO (chronic progressive ophthalmoplegia) and Kearns-Sayre syndrome (KSS) (52). [name] follows >20 patients with CPEO/KSS, and leads a national consortium (NAMDC – North American mitochondrial disease consortium) where >70 patients with CPEO/KSS have consented to be contacted for research. From this group, patients who have previously had diagnostic testing confirming the presence of mtDNA single deletion will be identified and invited to participate in the study.

Individuals without a confirmed genetic test who are otherwise eligible and who have family members with single large-scale mitochondrial DNA deletions and/or suspect they have the deletion will be invited to provide a buccal or urine sample to test for mitochondrial mutations. The genetic counselor or physician will review the specific consent form for genetic testing [Genetic Testing Consent Form MiSBIE], and sample collection instructions remotely with these participants or at the Columbia University Irving Medical Center research site.

Sample #3

Sample subject population:

Protocol Summary Form

Subject Population	Number of completers required to accomplish study aims	Projected number of subjects who will be enrolled to obtain required number of completers	Age range of subject population
Controls	100	118 (accounting for 10% attrition or unusable data n=10 and pilot testing n=8)	18 to 60

Description of subject population:

We will study healthy individuals without a diagnosis of mitochondrial disease recruited from the community. These participants will be age-, sex- and physical activity level- matched to participants from Groups 1 and 2.

Sample #4

Sample subject population:

Subject Population	Number of completers required to accomplish study aims	Projected number of subjects who will be enrolled to obtain required number of completers	Age range of subject population
Individuals with the m.3243A>G mitochondrial DNA mutation with MELAS symptoms. This is the same diagnostic group as Group 1, with the exception that patients who have experienced stroke-like episodes or seizures will not be excluded	30	33 (accounting for 10% attrition or unusable data)	18 to 60

New York State
Psychiatric Institute
Institutional Review Board
 PRISM 2022

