Protocol Summary Form

Description of subject population:

We will investigate individuals carrying the m.3243A>G tRNA^{Leu(UUR)} mutation who have experienced stroke-like episodes, seizures, or both which characterize MELAS (Mitochondrial Encephalopathy, Lactic Acidosis, and Stroke-like episodes) (50, 51). From this cohort and the existing patient registry, individuals who have previously had genetic diagnostic testing confirming the presence of the m.3243A>G will be identified and invited to participate in the study.

Individuals without a confirmed genetic test who are otherwise eligible and who have family members with 3243A>G mitochondrial DNA mutation with MELAS and/or suspect they have the mutation with MELAS will be invited to provide a buccal or urine sample to test for mitochondrial mutations. The genetic counselor or physician will review the specific consent form for genetic testing [Genetic Testing Consent Form MiSBIE], and sample collection instructions remotely with these participants or at the Columbia University Irving Medical Center research site.

Inclusion/Exclusion Criteria

Groups 1 (m.3243A>G) & 2 (single mtDNA deletion)

CRITERION	METHOD OF ASCERTAINMENT
Inclusion:	
1. Patients between the age of 18-60.	Patient clinical records Phone screen or clinical evaluation
2. Willing to provide saliva samples and have venous catheter installed for blood collection during the hospital visit	Phone screen or clinical evaluation
3. Willing to provide informed consent and capacity to consent	Self report
4. Use of effective method of birth control for women of childbearing capacity	Phone screen or clinical evaluation
5. Harbours a mtDNA mutation. Either the m.3243A>G point mutation, or a single large scale mtDNA deletion.	Patient clinical records, or family history involving them as “obligate carrier” of the mtDNA defect
6. English Speaking	Self report Phone screen or clinical evaluation
7. Confirmatory genetic test or willing to undergo genetic testing if one is not available.	
Exclusion:	
1. Patients with cognitive deficit incapable of providing informed consent will not be included	TICS scores ≥ 30 , administered via phone screen or clinical evaluation
2. Neoplastic disease	Patient clinical records, and self-report

Protocol Summary Form

3. Symptoms of flu or other seasonal infection four weeks preceding hospital visit, as this would influence immune system parameters	Phone screen or clinical evaluation

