4. Strokes & seizures.	Patient clinical records, and self-report
5. Raynaud's syndrome (Raynaud phenomenon)	Phone screen or clinical evaluation
6. Involvement in any therapeutic trials listed on clinicaltrials.gov, including exercise	Phone screen or clinical evaluation
7. Clinical use of steroid therapy, which would impact the HPA-axis and other physiological systems (e.g., oral dexamethasone, prednisone, or similar)	Patient clinical records Phone screen or clinical evaluation

Group 3 (Controls)

CRITERION	METHOD OF ASCERTAINMENT
Inclusion:	
1. Individuals between the age of 18- 60.	Patient clinical records Phone screen or clinical evaluation
2. Willing to provide saliva samples and have venous catheter installed for blood collection during the hospital visit	Phone screen or clinical evaluation
3. Willing to provide informed consent and capacity to consent	Self report
4. Use of effective method of birth control for women of childbearing capacity	Phone screen or clinical evaluation

Protocol Summary Form

5. English Speaking	Self report, Phone screen or clinical evaluation
Exclusion:	
1. Individuals with cognitive deficit incapable of providing informed consent will not be included	TICS scores ≥ 30 , administered via phone screen or clinical evaluation
2. Symptoms of flu or other seasonal infection four weeks preceding hospitalvisit, as this would influence immune system parameters	Phone screen or clinical evaluation
3. Raynaud's syndrome (Rayneau phenomenon)	Phone screen or clinical evaluation
4. Involvement in any therapeutic trials listed on clinicaltrials.gov, including exercise	Phone screen or clinical evaluation
5. Metal inside or outside the body or claustrophobia prohibitive to MRI testing	Phone screen or clinical evaluation
6. Diagnosed with mitochondrial disease m.3243A>G, or large scale mtDNA deletion	Phone screen or clinical evaluation

Group 4 (m.3243A>G with MELAS symptoms

CRITERION	METHOD OF ASCERTAINMENT
Inclusion:	
1. Patients between the age of 18- 60.	Patient clinical records Phone screen or clinical evaluation

Protocol Summary Form

2. Willing to provide saliva samples and have venous catheter installed for blood collection during the outpatient visit	Phone screen or clinical evaluation
3. Willing to provide informed consent and capacity to consent	Self-report and clinician assessment
4. Use of effective method of birth control for women of childbearing capacity	Phone screen or clinical evaluation

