5. Carries the m.3243A>G point mutation and has had at least one stroke-like episode, seizure, or both.	Patient clinical records, or family history involving them as "obligate carrier" of the mtDNA defect
6. English Speaking	Self-report Phone screen or clinical evaluation
7. Confirmatory genetic test or willing to undergo genetic testing if one is not available.	Medical Records Genetic Test
Exclusion:	
1. Patients with cognitive deficit incapable of providing informed consent will not be included	TICS scores \geq 30, administered via phone screen or clinical evaluation
2. Neoplastic disease	Patient clinical records, and self-report
3. Symptoms of flu or other seasonal infection four weeks preceding hospital visit, as this would influence immune system parameters	Phone screen or clinical evaluation
4. Raynaud syndrome (Raynaud phenomenon)	Phone screen or clinical evaluation

Protocol Summary Form

5. Involvement in any therapeutic trials listed on clinicaltrials.gov, including exercise	Phone screen or clinical evaluation
6. Clinical use of steroid therapy, which would impact the HPA-axis and other physiological systems (e.g., oral dexamethasone, prednisone, or similar)	Patient clinical records Phone screen or clinical evaluation

Study Procedures

We will only recruit and see one participant per week, as per the standard MiSBIE protocol. This low scheduling frequency eliminates any possible exposure between participants.

The study will unfold in two visits, distributed over two consecutive days. For review purposes, the study “Data Collection Form” (Appendix #5) in addition to a Study diagram summarizing study procedures in chronological order (Figure 1), are uploaded with this protocol. Breaks have been built into the study protocol, and participants are free to request breaks at any time. The study procedures comprise eight parts:

Participants who have family member with 3243A>G mitochondrial DNA mutation or deletion and/or who suspect they have the mutation or deletion will be asked to confirm through genetic testing prior to participation. [name] will approach these patients with information regarding genetic testing. These participants will provide a buccal cell or urine sample to test for mitochondrial variants. This genetic testing procedures (consent, sample obtain, genetic consult) will occur online over video chat or at the research site. The

Protocol Summary Form

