- (1) Recruitment: Patients with mitochondrial disease and healthy age/sex/race/physical activity level-matched controls will be recruited. As part of existing clinical care, some patients will have undergone (a) neuropsychological assessment, (b) metabolic assessment and (c) structural magnetic resonance imaging (MRI) as part of the diagnostic services of the Clinical Research Center for Muscular Dystrophy and Related Diseases Laboratory. From this patient pool, those molecularly identified to carry mtDNA defects (m.3243A>G, single deletion) will be provided with a study brochure and invited to sign a form agreeing to be contacted for future research. Potential participants will be contacted directly by the clinical coordinator or study coordinator who will provide information concerning the MiSBIE study and assess inclusion/exclusion criteria over the phone or in person. Should potential participants be interested in the study, they will be forwarded consent forms for their review.

We will screen participants for COVID symptoms at the following timepoints: during the initial screening call: the Monday night before the participant arrives, the Tuesday morning of study activities and the Wednesday morning of study activities. We will take the participant's temperature before starting study activities. We have a no-touch thermometer used for other MiSBIE procedures and have the required expertise to perform this measure.

Protocol Summary Form

[figure not shown]

Figure 1. Diagram illustrating study design and workflow.

Protocol Summary Form

For participants who agree to participate in the study, the a 2-day visit at the Columbia University Irving Medical Center will be scheduled and transportation/lodging arranged. Outside participants will be housed at the Edge Hotel (Washington Heights, [name]), and given detailed instructions to follow prior to their arrival.

(2) Initial Blood Draw and Biological Samples Collection: On the first outpatient visit (Day 1), a fasting blood draw to index allostatic load and cell isolation for mitochondrial function measurements and DNA/RNA analyses. Participants will first arrive at the Division of Behavioral Medicine, Presbyterian Hospital, 15th floor at 9:00am and will be greeted by [name], the MiSBIE study coordinator. Participants will have been instructed not to eat or drink beverages other than water starting at midnight the previous day.

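### The control eligibility table does not ensure the healthy comparator the protocol describes: it omits three exclusions applied to patient groups and words a fourth too narrowly

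*Protocol*

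**What the plan says.** The control group is described in two places in the protocol. Description of Subject Population, Sample #3, reads: "We will study healthy individuals without a diagnosis of mitochondrial disease recruited from the community". Study Procedures, item (1) Recruitment, reads: "Patients with mitochondrial disease and healthy age/sex/race/physical activity level-matched controls will be recruited".

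The Group 3 table under Inclusion/Exclusion Criteria has five inclusions: age, willingness to give samples, consent, contraception and English. None of them requires good health. It has six exclusions: cognitive deficit, recent infection, Raynaud's, participation in a therapeutic trial, metal or claustrophobia that rules out MRI, and "Diagnosed with mitochondrial disease m.3243A>G, or large scale mtDNA deletion".

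The table for Groups 1 and 2 also lists "Neoplastic disease" (exclusion 2), "Strokes & seizures" (exclusion 4) and clinical use of steroids (exclusion 7, with the HPA axis given as the reason). The Group 4 table repeats the neoplasia and steroid exclusions. It reverses the stroke/seizure rule, because inclusion 5 reads: "Carries the m.3243A>G point mutation and has had at least one stroke-like episode, seizure, or both".

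The SAP's primary outcomes are salivary cortisol AUC and an allostatic load index, each compared between controls and participants with mitochondrial disease. For heart rate and letter fluency, the SAP states that the patient side combines the m.3243A>G, MELAS and deletion groups.

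**The concern.** The written rules are unequal on the two sides of the main comparison. A diagnosis of cancer removes a patient from any group but is not a listed ground for refusing a control. A stroke or seizure removes a patient from Groups 1 and 2 but not a control. Steroid therapy removes a patient from any group but not a control. The word healthy appears only in descriptive text, and no criterion defines it.

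Each gap bears on an outcome:

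- Allostatic load draws on immune, metabolic, hematological and neuroendocrine measures. The protocol already excludes recent infection in controls because of its immune effect, so leaving out neoplasia does not fit its own reasoning.
- The protocol itself says that steroid therapy affects the HPA axis, which is what the cortisol outcome measures.
- Stroke and seizure histories matter for the imaging in Aim 3 and for the neuropsychological scores. Controls also serve as the reference for the age adjustment of those scores.
- A control with a different mitochondrial defect would carry the exposure under study.

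**Working it through.** No figure in the plan depends on this point, so the check is a line-by-line comparison of the eligibility tables.

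| Exclusion | Groups 1 and 2 | Group 4 | Group 3 (controls) |
|---|---|---|---|
| Neoplastic disease | Yes (2) | Yes (2) | No |
| Strokes and seizures | Yes (4) | No; a stroke-like episode or seizure is required | No |
| Steroid therapy | Yes (7) | Yes (6) | No |
| Mitochondrial disease | Not applicable | Not applicable | Two named defects (6), against any diagnosis in the Sample #3 description |
| General good health | Not applicable | Not applicable | No criterion, although described as healthy |

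The control table is not simply a shortened patient table. It adds an MRI line that the patient tables lack and keeps the infection and Raynaud's lines. If the word healthy were the working screen, those two lines would hardly be needed. A coordinator who applies only the table has no listed ground for refusing a volunteer with neoplastic disease, epilepsy or a past stroke, or one taking steroids.

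**Illustration of scale for allostatic load.** The inputs are the reported Hedges' g of 0.52 (SAP, primary outcome 2) and two assumptions that the documents do not supply: a share p of controls with such a history, from 0.03 to 0.10, and a shift s of 1 SD upward in those controls.

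- Movement of the control mean = p × s: 0.03 × 1 = 0.03 SD, and 0.10 × 1 = 0.10 SD.
- The reported g would already contain this dilution, so the undiluted effect = 0.52 + p × s: 0.55 and 0.62.
- Share hidden = (p × s) / (0.52 + p × s): 0.03/0.55 ≈ 5%, and 0.10/0.62 ≈ 16%.

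Dividing by 0.52 instead would give about 6% and 19%, but that treats the observed effect as the undiluted one. The movement of the mean is proportional to s, so a smaller assumed shift gives a proportionally smaller movement. A shift in the other direction would reverse its sign.

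**The case against.** The strongest reply is that the Sample #3 description is current protocol text and already restricts controls to healthy people with no mitochondrial diagnosis. Admitting someone with another mitochondrial disease would contradict it. Control exclusion 6 is ungrammatical as printed, and one comma after the word disease would make it agree with the description. The study is a single programme that sees one participant a week, and the phone-screen form, which may ask more, is not among the documents. All of this stands. It means that the table fails to spell out the description, not that the screening failed.

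The stroke/seizure rule also serves partly to separate Group 4 from Group 1. The SAP's letter-fluency comparison includes MELAS patients, so such histories are not barred from the patient side there. That stands too, and it limits this asymmetry to Groups 1 and 2. The SAP gives no connectivity analysis against which an effect on Aim 3 could be checked.

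The Day 1 medical examination is not stated to be for patients only. One of its forms covers clinical history and comorbidities, and the scan includes T2 images intended to show lesions. Unsuitable controls may therefore be identifiable, although the documents give no rule for acting on what is found.

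A reader might go further and infer any of the following, none of which the documents support:

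- That unsuitable controls were enrolled. Nothing shows this.
- That a past, treated cancer would exclude a patient. The criterion names neoplastic disease and does not say whether history counts.
- That the reported allostatic load difference (p = 0.018) is an artefact. Under the illustration above the bias runs toward the null and could not have created it.
- That all the gaps make controls resemble patients. This is plausible for some histories but not shown, and the protocol does not state the direction of a steroid effect on cortisol.

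**Conclusion.** The control table does not ensure the comparator that the protocol describes. Neoplastic disease and steroid therapy are excluded in every patient group but not in controls. Strokes and seizures are excluded in Groups 1 and 2 but not in controls. Exclusion 6 can be read more narrowly than the Sample #3 text. The steroid gap is the most direct, because the protocol itself ties steroids to the axis measured by a primary outcome.

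The size and direction of any bias cannot be computed from the documents. The range of about 5% to 16% of the undiluted allostatic load effect is an illustration that rests wholly on the assumed 3% to 10% prevalence and 1 SD shift. This is a table to reconcile and a sensitivity analysis to run. It is not evidence against the reported results.

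**What to change.** Reconcile the Group 3 table with the Sample #3 description and the Recruitment text:

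- Add the neoplastic-disease and strokes/seizures exclusions as worded for Groups 1 and 2, with matching ascertainment (self-report, and records where they exist).
- Reword exclusion 6 so that it covers any diagnosed mitochondrial disease, including the two defects now named.
- Align the steroid line with the patient tables at the same time.

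For controls already enrolled, apply these rules to the medical history already taken, where available, and state for how many controls it is missing. Then report both primary outcomes, including AUCg and AUCi for cortisol, with and without the controls who fail. This matters most for AUCi, whose reported p-value of 0.049 leaves little room for change.

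The table change takes four lines and a few more questions in the existing phone screen, and somewhat more community volunteers will fail screening. The sensitivity analysis needs no new visits if controls completed the Day 1 history form. If that form does not record steroid use, that item would have to be reported as unknown.

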(5) Stress Reactivity–Recovery Paradigm: After the lunch, participants will have an IV line placed and be instrumented with physiological data acquisition equipment. Participants will be exposed to a standardized socio-evaluative laboratory challenge (58, 59). Participants will be asked to perform a simulated public speaking task, consisting of 2 min of preparation for a speech defending themselves against an alleged transgression followed by 3 min of videotaped speech delivery, as previously described (58, 59) (please find the protocol attached in Appendix #6). Throughout, we will collect repeated measures of blood (cortisol, ACTH, catecholamines, inflammatory cytokines), saliva (cortisol), and physiological monitoring (blood pressure, heart rate variability, galvanic skin response, and respiration). Research assistant [name] and [name] will monitor physiological data collection during the session and equip participants. This stress paradigm session consists of a five-part protocol:

(A) Participants will be equipped with:

Protocol Summary Form

- a. A 3-lead ECG to monitor of heart rate
- b. A finger cuff blood pressure sensor to monitor blood pressure
- c. Skin conductance surface device to monitor sympathetic nervous system activity (sweating)
- d. Two elastic breathing bands on the chest and abdomen.

(B) Participants will rest for 30 minutes in a calm room and asked to refrain from any other medium (e.g., smartphones) that could be a source of distraction. This will avoid to introduce variability in inter-individual responses. This will allow them to acclimate to their surroundings and to the equipment (e.g., ECG electrodes, finger cuff).

(C) Participants will be exposed to a socio-evaluative stress (58, 59) that induces significant psychophysiological responses among multiple systems. Psychosocial stress is induced by simulating videotaping and that these video recordings will be analyzed for speech performance by comparing their performance with those of other participants. Eight (10) mL of blood for plasma (5ml) and serum (5ml) will be collected via the venous catheter at eight defined time-points relative to the onset of the SECPT (-5, +5, +10, +20, +30, +60, +90 and +120 minutes), for a total of 80 mL of blood. Time points are illustrated in Figure 2.

[figure not shown]

Figure 2. Expected kinetics of stress biomarkers after the socio-evaluative stress. BP = blood pressure; CORT = cortisol; E = epinephrine; HR = heart rate; IL-6 = interleukin-6; NE = norepinephrine.

Affect ratings will be collected at each time point on an iPad to measure subjective feelings of positive and negative affect (calmness and nervousness, see attached in appendix #1.3).

Protocol Summary Form

In addition, 1 mL of saliva will be collected with salivettes (Starsted) at each time point. A sterile cotton swab will be introduced in the participant's mouth, soaks with saliva for a period of approximately 2-3 minutes, and is placed back into the tube for subsequent saliva extraction by centrifugation. Oral (sub- lingual) and epidermal (anterior part of neck, back of the dominant hand) temperature will be measured non-invasively at the same time points using a no-touch infrared thermometer (AccuMed AT2102 or HTD8808) to detect thermal changes during stress reactivity and recovery.

At the last time point (+120 minutes), an additional 8.5 mL of blood will be collected to isolate PBMCs to assess effects of stress on epigenetic modifications of DNA and gene expression on sub-populations of cells and one EDTA coated tube (2ml) for complete blood count on whole blood, which totals 10.5ml.

Total blood volume drawn including the fasting morning collection and stress reactivity is approximately 190.5 mL (100 mL baseline for AL, mitochondrial function, and DNA/RNA) + (10 x 8 = 80 mL for stress reactivity biomarkers) + (10.5 mL for DNA/RNA)]. This volume does not exceed the prescribed limit for adult individuals above 110lb of body weight (200mL), and it is less than half the volume of a standard blood donation (approximately 500 mL). After the 120min time point, the venous catheter will be removed.

(D) Deep breathing: Five minutes later, participants will be asked to perform a paced deep breathing exercise with visual feedback lasting two minutes while heart rate is recorded. This will enable assessment of autonomic regulation through breathing.

(E) Standing: Sit-to-stand posture changes elicit changes in heart rate and blood pressure. Participants will be asked to go from the sitting position and stand for 5 minutes. Then sit down again.

(F) Functional capacity: Participants will then be asked to stand as many times as they can, as quickly as possible over the course of 30 seconds. This simple 30 second sit-to-stand test is used to measure functional capacity.

Respiratory rate, heart rate, blood pressure, and skin conductance will be continuously recorded.

If the participant's gait is unsteady or if participants are known to have ataxia or other movement abnormalities, an additional study personnel will be in the room to spot the participant during this task.

(G) Cold pressor test: Participants will be asked to immerse their right hand up to and

Protocol Summary Form

including the wrist into a bucket filled with ice cold water ($4\pm0.5^{\circ}\text{C}$) for 90 seconds (60). This will be followed by a 10-minute recovery period after which a saliva sample will be collected.

(H) Metabolic Rate Analysis: Participants will then be asked to breathe normally into the ReeVue, a device that measures basal metabolic rate, for 10 minutes. The device analyzes oxygen consumption and uses standard algorithms to convert oxygen consumption to metabolic rate or energy consumption.

The ReeVue breathing hose is specifically designed with a one-way valve such that participants breathe in from the room and out through the device, thus avoiding exposure to any particles from the device. All participants will use a new, disposable breathing tube and nose clip during data collection.

(I) Participants will (a) be de instrumented of equipment.

For most of the afternoon protocol, only 1 researcher will be in the lab space with the participant. The only exception to this is during periods where the nurse will collect a blood sample at the same time as the study coordinator is collecting a saliva sample. This timing is imperative to the study design of this protocol.

The participant will be stationary and instrumented with physiological equipment for the course of the afternoon.

Time estimation task: After being de-instrumented, participants will take part in a time estimation task. For the first part of this task, the coordinator sets a buzzer for a certain number of seconds, and the participant must estimate how much time has passed. For the second part of the task, the participant must say when a certain amount of time has passed. Each of the two parts consists of 10 brief trials of 10, 30, or 60 seconds. In total, this task takes about 20 minutes.

Early MiSBIE participants who did not complete this task during their visit will be recontacted to complete the task over password-protected video call. Calls will take places between 3PM-5PM to replicate timing during normal study procedures.

(6) Urine collection: At the end of the Day 1 visit, participants will be provided with a designated container to collect overnight urine. The container contains a small amount of acetic acid to preserve catecholamines. Participants are provided with a disposable plastic cup(male) or a urine hat(female) and instructed to urinate in the cups, and then pour their

Protocol Summary Form

content into the larger container to avoid any potential skin contact with the preservative. The target period will be from 8pm to 8am (12 hours) between Day 1 and 2. The container will be provided into a large sealed “Ziplock” bag and in an opaque tissue bag for transportation. This prevents undesirable odors and minimize psychological discomfort or stigmatization that could be associated with this task. An instructions sheet (attached for review in appendix #1.4) will be provided to all participants along with the container at the end of Day 1. Urine will be processed and biomarkers analyzed on site.

DAY 2

The urine container will be received, and compliance assessed.

(7) Metabolic Rate Analysis: Participants will be asked to breathe normally into the ReeVue for 10 minutes. This will give us information about the participant’s resting metabolic rate.

(8) Questionnaires and Neuropsychological Assessment: The participant will be asked to complete a few questionnaires on paper at the hotel both at the day of arrival and at the end of Day 1 (Package #1 and #2). After the breakfast and between the +60 and +120 minute time points of the stress reactivity protocol, participants will complete a small questionnaire package (listed in the “Assessment Instruments” section, Package #3 and #4) on an electronic device (iPad) via an encrypted online system (RedCap) to assess psychosocial variables. Two RedCap projects will be created to manage data: one for screening of potential participants, and one for enrolled participants. RedCap will be used throughout the study to store and export data for analyses.

For participants who have visual processing difficulties, questions can be read aloud to the participant by either the coordinator or caregiver.

On Day 2, participants will also complete another set of questionnaires listed in the “Assessment Instruments” section (Package #5) via RedCap. The participant will be alone while completing the questionnaire package.

Some of the questions included in these questionnaires address suicidal ideation. To assess participant safety, we will monitor participant responses to these questions. If the participant indicates 1 (I have thoughts of killing myself but would not carry them out) on Beck Depression Inventory (BDI) (Day 2 Part 2) plus a moderate BDI score (17 or over) OR Participant rates a 2 (I would like to kill myself on BDI) the study coordinator will follow a series of questions to assess risk. If the participant indicates they have a plan, contact [name], if he is unreachable contact [name]. If the participant indicates, they have the means and/or a timeframe in mind, this indicates serious risk and the study coordinator will remain with the participant at all times and contact [name].

Protocol Summary Form

In addition, a compliance form will be submitted to the participants at the beginning of Day 1 and Day 2 to ensure they followed the instructions (please see attached in appendix 8 and 9).

Neuropsychological functioning will be assessed by a trained study coordinator using the following instruments:

Measure	Description	Time (minutes)
Wechsler Abbreviated Test of Intelligence (WASI-II) (54)	Estimate of current intellectual function	20
Vocabulary		
Matrix Reasoning		
Neuropsychological Assessment Battery (NAB) (55)		10
Digits Forward and Backward	Working memory	
Shape Learning	Visual learning and memory	
Numbers and Letters	Selective and divided attention	
Repeatable Battery for the Assessment of Neuropsychological Status (RBANS) (56)		20
Line Orientation	Visual spatial skills	
List Learning	Verbal learning and memory	
Picture Naming	Word generation	
Coding	Processing speed	
List Recall	Delayed Memory	
List Recognition	Delayed Recognition	
Delis-Kaplan Test of Executive Functions (D- KEFS) (57)		38
Trail Making	Working memory, cognitive flexibility and speed	
Verbal Fluency	Language production	
Color-Word	Inhibition	

Protocol Summary Form

Sorting	Mental flexibility and conceptualization	
Test of Premorbid Functioning (TOPF)	Estimate of premorbid intellectual function	2
		90

(9) **Brain Imaging:** On the second outpatient hospital visit (Day 2) that will take place at the Mortimer B. Zuckerman Mind Brain Behavior Institute (ZMBBI), we will collect fMRI-BOLD data during psychological tasks and rest. ZMBBI now sanitizes the MRI machine before and after each participant. Specifically, we will administer three tasks to assess function of the putative threat/salience network (61, 62), or brain appraisal system (63), a neural network showing stress-related activity that includes the amygdala, anterior cingulate cortex, and hippocampus.

Magnetic resonance imaging will be used with a protocol consisting of one structural scan of high-resolution T1-weighted images, and fMRI blood oxygen level-dependent imaging (BOLD) will be employed over task runs consisting of T2*weighted gradient-echo images. Scanning will take place on a GE MR750 3 Tesla scanner at ZMBBI. These techniques were selected as they are non-invasive and widely used, ideally suited to evaluate functional connectivity, and they will provide measurements built on the previous literature.

Participants will be escorted to ZMBBI on the second day of the study, on the first floor. Upon arrival, participants will be ushered by the study coordinator to a private waiting room in the MRI suite on the basement floor of the ZMBBI building. The urine container will be received, and compliance assessed.

Five minutes after arriving, 1 mL of saliva will be collected with a salivette, as per the previous day. Affect ratings (4 questions) will also be collected, as per the previous day.

For female participants, a pregnancy test will be performed because of potential unknown long-term effects of MRI on fetal development. Participants who refuse to take a pregnancy test prior to the start of the MRI scan for any reason they will forgo their participation in the MRI.

The scanning protocol will last 1.5 hours, including all scanning sequences and set up of the participant in the scanner suite. The participant will be positioned on the MRI table, using a plastic head-holder to decrease head movement during the scan. Participants will be given foam earplugs to reduce the noise of the MRI as well as a MRI-compatible hand held

Protocol Summary Form

response pad.

A three-lead ECG will be connected to participants to monitor heart rate responses in conjunction with brain activation.

The task instructions will be projected from a liquid crystal display projector zoomed to a screen inside the MR suite or viewed through dual channel binocular goggles. Functional fMRI-BOLD images will be acquired.

To account for the accessibility needs of patients with visual processing issues or ophthalmoplegia, instructions and text during scanning will be read aloud by the coordinator.

During each pause between acquisitions, the participant is asked to rate their physical discomfort on a scale of 0-10. If the score rises above 5, the coordinator pauses the session and asks if the participant wishes to continue or if any adjustments can be made (i.e. change in position, an additional blanket for warmth, a sitting break).

As on Day 1, at three time points during the MRI imaging session saliva samples will be collected, along with affect ratings (5 questions).

These fMRI tasks will be administered in the following order:

Saliva sample and affect rating #10

(A) *Localizer (1 run, 1 min)*

Localizing of brain and defining region of interest.

(B) *Field map (1 run, 1 min)*

Acquisition of field map for multiband correction.

(C) *T2 scan (1 run, 12 min)*

T2-weighted images for detection of potential lesions and ventricles. This scan will be collected as participants are instructed to "rest and allow their minds to wonder and not to think of anything in particular". Participants are also instructed not to fall asleep.

(D) *T1 structural scan (1 run, 5 min)*

T1-weighted images for anatomical co-registration. This scan will be collected as participants are instructed to "rest and allow their minds to wonder and not to think of anything in particular".

(E) *Multisensory (1 run, 5 min)*

Protocol Summary Form

Participants will be trained and later exposed to the multisensory task. This task consists of visual (checker board), auditory stimulation (constant pitch sound), button push on the button box.

(F) Resting State Run #1 (1 run, 11 min)

This scan will be collected as participants are instructed to “rest and allow their minds to wonder and not to think of anything in particular”. Participants are reminded not to fall asleep.

Saliva sample and affect rating #13

(G) N-back task Run #1 (1 run, 6 min)

This working memory task (64) consists of 9 blocks presented in ABBA or BAAB order, interspersed by 25 s of resting fixation. On each of 360 trials, a word is presented for 2 s followed by an inter-stimulus-interval fixation cross for 1 s. Participants are instructed to respond as quickly and accurately as possible to each word with a button press indicating, “yes, this word matches the word presented n-trials ago” (a target response) or “no, this word does not match the one presented n-trials ago” (a nontarget response). The first 3 trials of each block are not included in the analysis; these trials are always nontargets in the 3-back block and therefore did not carry the same task demand as the remaining trials.

(H) N-back task Run #2 (1 run, 6 min)

This is the second run of the N-back task. Instructions are the same as in “G”.

(I) Socio-evaluative Task (1 run, 6 min)

The procedure will be the same as in day 1 except subjects will be told that their “performance on the first speech task was slightly below average when compared with other participants’ speeches” and participants will be asked to “try to be more persuasive when delivering this speech”. They will be told that the speech will be delivered after the scan session to the expert who evaluated you yesterday. At the end of the task, participants will be told that they were randomly selected not to give their speech, as in previous work. A pulse oximeter will be hooked up to participants, and heart rate responses in conjunction with brain activation will be assessed

(J) Cold Pressor Task (1 run, 6 minutes)

This is a modified task from the cold pressor administered on Day 1. Participants will be instrumented with a thermal arm wrap designed specifically for the MRI environment and will be instructed as follows: “We will place this arm wrap around your hand and arm. It is quite cold and may be uncomfortable, but it will not injure you.” The arm wrap is a fabric-based foldable unit fitted with Velcro attachments

for detachable gel packs, which are kept in a temperature-controlled freezer prior to the procedure. Five (5) minutes before the procedure, gel packs are removed from the freezer, attached to the arm wrap, and layered with two layers of waterproof film paper to adjust immediate contact temperature to safe but uncomfortable -2 ± 2 degrees Celsius, as previously described (65, 66).

(K) Diffusion Tensor Imaging – DTI (Seq 1-2, 6 min)

